## 3 Study design

This is a non-randomized, open-label, multi-center, phase II study to assess the efficacy and safety of eltrombopag in Chinese subjects with severe aplastic anemia who had insufficient

response or relapsed following at least one treatment course in the period time of  $> 6$  months of immunosuppression with a regimen containing anti-thymocyte globulin (ATG), anti-lymphocyte globulin(ALG), and/or cyclophosphamide, or alemtuzumab. The study design is shown in [Figure 3-1](#).

As this is a bridging study to support China registration, an estimation strategy rather than formal hypothesis testing will be pursued. Approximately 20 subjects will be enrolled into the study based on feasibility and statistical considerations.

Treatment with eltrombopag will be started at 25 mg/day and increased by 25 mg/day every 2 weeks according to the platelet count up to 150 mg/day (Refer to [Section 6.5.1](#)). Hematological response rate will be assessed at 3, 6 months and 1 year after starting the study treatment (Week 13, 26 and 52).

The primary endpoint is the hematologic response rate (defined as the proportion of subjects who meet any of the IWG response criteria) at Week 26. Subjects in whom the treatment is assessed as effective (meet any of the response criteria) at 6 months will continue the study treatment.

Eltrombopag should be discontinued if the treatment is assessed as ineffective at 6 months in order to avoid continuing treatment aimlessly. Subjects are allowed to discontinue eltrombopag before 6 months if any of the treatment discontinuation criteria described in [Section 9.1.1](#) is met.

[figure not shown]

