#### 6.1.5 Treatment duration

If the subject fails to response after 6 months (26 weeks), he/she will discontinue eltrombopag treatment. Responding subjects who are considered to require continued treatment at Week 52 will be provided with continued treatment up to the launch of the product after approval of the investigated indication or until the end of the study.

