2.1.2 General analysis conventions

Pooling of centers: Unless specified otherwise, data from all study centers will be pooled for the analysis. Due to expected small number of patients enrolled at centers, no center effect will be assessed.

Qualitative data (e.g., gender, race, etc.) will be summarized by means of contingency tables; a missing category will be included as applicable. Percentages will be calculated using the number of patients in the relevant population or subgroup as the denominator.

Quantitative data (e.g., age, body weight, etc.) will be summarized by appropriate descriptive statistics (i.e. mean, standard deviation, median, minimum, and maximum). PK parameters except Tmax will be summarized by appropriate descriptive statistics (n, arithmetic

mean, CV% mean, standard deviation (SD), median, geometric mean, CV% geo-mean, minimum and maximum).

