2.1.3 General definitions

Study drug and Study treatment

The study drug/study treatments for this study is eltrombopag (ETB115).

Eltrombopag will be supplied as film-coated tablets (25 mg) provided either as commercial packages locally.

Date of first administration of study treatment

The date of first administration of study treatment will be derived as the first date when a nonzero dose of study treatment is administered and recorded on the appropriate CRF.

Date of last administration of study treatment

The date of last administration of study treatment will be derived as the last date when a nonzero dose of study treatment is administered and recorded on the appropriate CRF. For those patients still on treatment at cutoff date, the cutoff date will be imputed as the date of last administration of study treatment.

Study day

The study day, describes the day of the event or assessment date, relative to the reference start date.

The study day is defined as:

- The date of the event (visit date, onset date of an event, assessment date etc.) – reference start date + 1 if event is on or after the reference start date;
- The date of the event (visit date, onset date of an event, assessment date etc.) – reference start date if event precedes the reference start date.

The reference date for all assessments (safety, efficacy, pk, etc) is the date of first administration of study treatment as defined above. The study day will be displayed in the data listings.

Time unit

A year length is defined as 365.25 days. A month length is 30.4375 days (365.25/12). If duration is reported in months, duration in days will be divided by 30.4375. If duration is reported in years, duration in days will be divided by 365.25.

Baseline

For safety and efficacy evaluations, the last available assessment on or before the date of first administration of study treatment is defined as “baseline” assessment. If patients have no value as defined above, the baseline result will be missing.

On-treatment assessment/event and observation periods

The overall observation period will be divided into three mutually exclusive segments:

1. ***pre-treatment period***: from day of patient's informed consent to the day before first administration of study treatment
2. ***on-treatment period***: from date of first administration of study treatment to 30 days after date of last actual administration of study treatment (including start and stop date)

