2.8 Safety analyses

All safety analyses will be based on the safety set.

The safety summary tables will include on-treatment assessments collected no later than 30 days after last dose of study treatment (see definition in [Section 2.1.1](#)).

All safety assessments will be listed by patient and flagged appropriately.

All safety assessments will be generated for the final CSR except for subgroup of interest.

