2.8.1 Adverse events (AEs)

Coding and grading

Adverse events will be coded using the Medical dictionary for regulatory activities (MedDRA) Terminology and their severity assessed according to the Common Terminology Criteria for Adverse Events (CTCAE) version 4.03.

General rules for AE Reporting

AE summaries will include all AEs occurring during on treatment period. All AEs collected in the AE (e)CRF page will be listed along with the information collected on those AEs e.g. AE

relationship to study drug, AE outcome etc. AEs with start date outside of on-treatment period will be flagged in the listings.

AEs will be summarized by number and percentage of subjects having at least one AE, having at least one AE in each primary system organ class (SOC) and for each preferred term (PT) using MedDRA coding. A subject with multiple occurrences of an AE will be counted only once in the respective AE category. A subject with multiple CTCAE grades for the same preferred term will be summarized under the maximum CTCAE grade recorded for the event. AE with missing CTCAE grade will be included in the 'All grades' column of the summary tables.

In AE summaries, the primary system organ class will be presented alphabetically and the preferred terms will be sorted within primary SOC in descending frequency. The sort order for the preferred term will be based on their frequency.

The following adverse event summaries will be produced for AEs occurring during the on-treatment period; overview of adverse events and deaths, AEs by SOC and PT, summarized by maximum CTCAE grade, summarized by relationship (all AEs and AEs related to study treatment), seriousness (SAEs and non-SAEs), leading to treatment discontinuation, leading to dose interruption/changes, requiring additional therapy and leading to fatal outcome.

Furthermore, AE occurring during the on-treatment period will be summarized by subgroup defined by age group (<65 years and \geq 65 years), gender (male and female) and concomitant use of CsA and anabolic steroids at baseline (Yes and No) (see [Section 2.2.1](#)). These summaries include: AEs by SOC and PT, AEs with suspected relationship to study drug by SOC and PT and SAEs by SOC and PT. These subgroup analysis will not be reproduced for final CSR.

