In addition, on treatment adverse events will be summarized by SOC and PT and by periods (by \leq 30 days, $>$ 30 to \leq 90 days, $>$ 90 to \leq 180 days, $>$ 180 to \leq 270 days, $>$ 270 to \leq 360 days, and $>$ 360 days). Time of onset of first episode will be used when experiencing the same episode in a subject.

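### The by-period adverse event table names no denominator; under the SAP's default, percentages after Week 26 understate risk among subjects still on treatment

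*SAP*

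**What the plan says.** SAP 2.8.1 plans an additional table in which "on treatment adverse events will be summarized by SOC and PT and by periods". The cut points are 30, 90, 180, 270 and 360 days, and the last column is open-ended. Repeated events are handled by one rule: "Time of onset of first episode will be used when experiencing the same episode in a subject". No denominator, number at risk or person-time is given for the columns.

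Three other statements supply the default:

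- SAP 2.8.1, general rules: "AEs will be summarized by number and percentage of subjects having at least one AE".
- SAP 2.1.2: "Percentages will be calculated using the number of patients in the relevant population or subgroup as the denominator".
- SAP 2.8: "All safety analyses will be based on the safety set". SAP 2.2 makes this set identical to the Full Analysis Set, that is, the treated subjects.

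The protocol ends treatment for non-responders part-way through these periods. Protocol 6.1.5 says "If the subject fails to response after 6 months (26 weeks), he/she will discontinue eltrombopag treatment", and Protocol 3 says "Eltrombopag should be discontinued if the treatment is assessed as ineffective at 6 months". SAP 2.1.3 defines the on-treatment period as running "from date of first administration of study treatment to 30 days after date of last actual administration of study treatment".

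**The concern.** A programmer who follows the SAP would divide by the same N in all six columns. From about Day 213, non-responders can no longer contribute an on-treatment event, yet they stay in that N. Under the plan's own 40% assumption they are the majority of the study, and they leave because the protocol requires it.

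A by-period table is read from left to right to see whether events become rarer with longer treatment. With a fixed denominator, exits alone can produce a fall. Safety and tolerability is a secondary objective and the study supports registration. SAP 2.8 regenerates the safety outputs, apart from subgroups, for the final report, when extension data fill the last column.

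For Week 52 response, SAP 2.7.3 removes ongoing subjects who have not yet reached the time point. The adverse event table has no matching rule. At the primary analysis, therefore, late enrollees with little more than 26 weeks of follow-up would also sit in denominators for time not yet observed.

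**Working it through.** **Inputs**

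- Planned N = 20 and assumed response 40% (SAP 3 and 3.1), so 8 continue and 12 stop.
- Other response rates: 20%, 30% and 50% (SAP Table 3-1); 47.6% (Japanese study, Protocol 1.2).
- Week 26 = Day 183 (Protocol Table 8-1); response window Day 168 to 196 (SAP Table 2-1).
- On-treatment tail: 30 days after last dose (SAP 2.1.3).
- Assumptions, because the documents give no figures: responders stay on treatment; no one leaves before Day 180 (0 to 4 early exits shown below).

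**The plan's own figure.** The documents compute nothing for adverse events by period. Their only figure based on the response rate is the 90% Clopper-Pearson interval. For 8/20 this gives 21.7% to 60.6%, and the largest half-width, at 10/20, is (69.8 − 30.2)/2 = 19.8 points. Both agree with SAP 3.1.

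**When non-responders leave.** 183 + 30 = Day 213. Across the window: 168 + 30 = Day 198 to 196 + 30 = Day 226. All of these fall inside the >180 to 270 day column.

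**Periods up to Day 180.** All 20 are on treatment, so the factor is 1.0.

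**>270 to 360 days, and the start of >360 days.** Factor = all treated / still on treatment.

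| Response rate | Still on treatment | Factor |
|---|---|---|
| 20% | 4 | 20/4 = 5.0 |
| 30% | 6 | 20/6 = 3.3 |
| 40% | 8 | 20/8 = 2.5 |
| 47.6% | 9.52 | 20/9.52 = 2.1 |
| 50% | 10 | 20/10 = 2.0 |

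Beyond the start of the last column the factor grows as responders leave.

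**>180 to 270 days.** By number on treatment at the start, 20/20 = 1.0. By person-time, factor = (20 × 90) / person-days on treatment, at 40% response:

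| Stop day | Person-days | Factor |
|---|---|---|
| 168 | 8×90 + 12×18 = 936 | 1800/936 = 1.92 |
| 183 | 8×90 + 12×33 = 1116 | 1800/1116 = 1.61 |
| 196 | 8×90 + 12×46 = 1272 | 1800/1272 = 1.42 |

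If 2 or 4 non-responders leave before Day 180 (stop day 183), person-days are 720 + 10×33 = 1050 or 720 + 8×33 = 984, and the factor is 1.71 or 1.83.

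**What the table would show.** Suppose the true risk is a constant 25% per 90 days on treatment.

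- >180 to 270 days: the 12 non-responders have 33 days each, with risk 1 − 0.75^(33/90) = 10.0%. Expected subjects: 8×0.25 + 12×0.100 = 3.2, shown as 3.2/20 = 16%.
- >270 to 360 days: 8×0.25 = 2, shown as 2/20 = 10%.

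A constant risk therefore appears as 25%, 16%, 10%.

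**Precision.** Two subjects with first onset in >270 to 360 days give 2/20 = 10% (90% CI 1.8% to 28.3%) or 2/8 = 25% (4.6% to 60.0%).

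**The case against.** The strongest reply is that SAP 2.8.1 never states an all-treated denominator. The wording of SAP 2.1.2 about the relevant population or subgroup could be read as subjects on treatment in the period. That is possible, but no such subset is defined, and SAP 2.8 points to the safety set. All-treated is the likelier reading, though it remains an inference.

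Second, n/20 is a correct proportion of treated subjects with first onset in that period. This stands. It misleads only when columns are compared over time or read as risk among those still treated.

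Third, attrition is partly visible elsewhere. SAP 2.3.5 tabulates disposition, SAP 2.4.1 groups exposure at 13, 26 and 52 weeks, and all events are listed. This softens the problem, but those cut points do not match the adverse event periods, and no per-period N or person-time is planned.

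Fourth, this is a supplementary descriptive table in an estimation study of about 20 subjects. That limits the consequence and is accepted.

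A reader might also infer three stronger things that the documents do not support:

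- **Every late column is understated 2.5-fold.** The 30-day tail keeps all 20 on treatment at the start of >180 to 270 days, so that factor is lower.
- **Any fall over time is due only to exits.** The first-episode rule also moves counts into earlier periods, and a real decline would contribute too.
- **Long-term tolerability is itself a stated objective.** The objective is safety and tolerability in general; toxicity with extended treatment appears only in the rationale for duration (Protocol 4.2.2).

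**Conclusion.** The concern holds as a gap in specification whose default misleads. At 40% response the default percentages understate first-onset risk among subjects still treated by about 2.5-fold for >270 to 360 days and at the start of >360 days. The range is 2.0 to 5.0 for response rates of 50% to 20%. For >180 to 270 days the understatement is about 1.6-fold by person-time, and 1.4 to 1.9 across the Week 26 window. Columns up to Day 180 are unaffected if no one leaves early.

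These factors rest on the inferred denominator, on non-responders stopping as the protocol requires, and on responders staying on treatment. If responders also leave, the later factors rise. The 2.5 is 20/8 under a planning assumption; neither document states it.

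**What to change.** Amend SAP 2.8.1 in two steps.

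1. For each period, base percentages on subjects whose on-treatment period reaches the start of that period, and print this N in the column header.
2. For each period, add the number of subjects with a first event divided by total person-time on treatment in that period. State whether a subject's time for a given term ends at the first episode, as the first-episode rule implies.

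Step 1 alone is not enough. It leaves N near 20 for >180 to 270 days, where most exits occur part-way through, and it cannot equalise follow-up in the open-ended >360 day column. Step 2 is needed for both.

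The cost is two sentences, a changed header and some programming, with no new data and no change in trial conduct. Late-period figures become less favourable and less precise, as 2/8 against 2/20 shows. The overall adverse event incidence tables and all efficacy results stay the same. The SAP asks for analysis decisions before database lock; if lock has passed, the added output should be labelled as such.

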2.8.1.1 Adverse events of special interest / grouping of AEs

An adverse event of special interest is a grouping of adverse events that are of scientific and medical concern specific to compound eltrombopag. These groupings are defined using MedDRA terms, SMQs (standardized MedDRA queries), HGLTs (high level group terms), HLT (high level terms) and PTs (preferred terms). Customized SMQs (Novartis MedDRA queries, NMQ) may also be used. A NMQ is a customized group of search terms which defines a medical concept for which there is no official SMQ available or the available SMQ does not completely fit the need. It may include a combination of single terms and/or an existing SMQ, narrow or broad.

At the project level, a sas dataset named eCRS contains the exact composition of the adverse events groupings will be used to map reported adverse events to the notable adverse events groupings. This dataset may be updated (i.e., it is a living document) based on review of accumulating trial data, and it is the most up to date version at the time of DB lock that will be used. Note that certain adverse events may be reported within multiple groupings.

For each specified AESI, number and percentage of patients with at least one event of the AESI occurring during on treatment period will be summarized. Summaries of these AESIs will be provided by subgroup (see [Section 2.2.1](#)). A listing of all grouping levels down to the MedDRA preferred terms used to define each AESI will be generated.

2.8.2 Deaths

The number and percentage of deaths occurring during the on-treatment period and at any time during the study will be provided. Deaths occurring during the on-treatment period will be further summarized by system organ class and preferred term. All deaths will be listed and flagged appropriately.

2.8.3 Laboratory data

On analyzing laboratory data, data from all sources (central and local laboratories) will be combined. The summaries will include all assessments available for the lab parameter collected no later than 30 days after the last treatment administration date (see [Section 2.1.1](#)).

Hematology and clinical chemistry laboratory parameters

The following summaries will be produced for hematology and clinical chemistry laboratory data (by laboratory parameter):

- Worst post-baseline CTC grade (regardless of the baseline status). Each subject will be counted only for the worst grade observed post-baseline.
- Shift tables using CTC grades to compare baseline to the worst on-treatment value
- For laboratory tests where CTC grades are not defined, shift tables using the low/normal/high/(low and high) classification to compare baseline to the worst on-treatment value.
- Trends of lab parameter values over time (baseline and selected on-treatment timepoints) should be displayed via boxplots based on time windows and corresponding tables displaying the statistics used for the box plots by the selected time points and the selected lab parameters.

The following listings will be produced for the laboratory data:

- Listings of all laboratory data, with CTC grades and classification relative to the laboratory normal range. Lab data collected during the post-treatment period will be flagged.
- Listing of all CTC grade 3 or 4 laboratory toxicities

Coagulation

Coagulation assays data (Prothrombin time/international normal ratio, Activated partial thromboplastin time) will be listed.

Liver function parameters

Liver function parameters of interest are total bilirubin (TBL), ALT, AST and alkaline phosphatase (ALP). The number (%) of patients with worst post-baseline values as per Novartis Liver Toxicity guidelines will be summarized.

For summaries based on multiple parameters, the results must be obtained from samples collected within maximum 30 days of each other.

The following summaries will be produced:

- ALT or AST > 3xULN and TBL > 2xULN and (ALP < 2xULN or missing)
- ALT or AST > 3xULN and TBL > 2xULN
- ALT or AST > 3xULN and TBL > 1.5xULN
- ALT or AST > 20xULN
- ALT or AST > 10xULN
- ALT or AST > 5xULN
- ALT or AST > 3xULN
- ALT > 20xULN
- ALT > 10xULN
- ALT > 5xULN
- ALT > 3xULN
- AST > 20xULN
- AST > 10xULN
- AST > 5xULN
- AST > 3xULN
- TBL > 2xULN
- TBL > 1.5xULN
- ALP > 1.5xULN

2.8.4 Other safety data

2.8.4.1 ECG

A standard 12 lead ECG will be performed:

- at screening or baseline (Triplicate ECG to be collected to assess QTcF intervals)
- at Week 26 and Week 52
- at the end of treatment

Data handling

In case the study requires ECG replicates at any assessment, the average of the ECG parameters at that assessment should be used in the analyses.

Data analysis

The following summaries will be produced for ECG results:

- Shift tables using ECG findings to compare baseline to the Week 26, Week 52 and to the worst post-baseline results.
- Descriptive statistics including mean, SD, median, 25th and 75th percentiles, minimum, and maximum will be summarized for ECG values at each visit.
- The number and percentage of subjects with notable ECG values below at each visit will be presented.
 - QT, QTcF, or QTcB
 - New value of > 450 and ≤ 480 ms
 - New value of > 480 and ≤ 500 ms
 - New value of > 500 ms
 - Increase from Baseline of > 30 ms to ≤ 60 ms
 - Increase from Baseline of > 60 ms
 - HR
 - Increase from baseline $> 25\%$ and to a value > 100 bpm
 - Decrease from baseline $> 25\%$ and to a value < 50 bpm
 - PR
 - Increase from baseline $> 25\%$ and to a value > 200 ms
 - New value of > 200 ms
 - QRS
 - Increase from baseline $> 25\%$ and to a value > 120 ms
 - New values of QRS > 120 ms

A listing of all ECG assessments will be produced by treatment arm and notable values will be flagged. In the listing, the assessments collected during the post-treatment period will be flagged.

2.8.4.2 Vital signs

Vital sign assessments are performed in order to characterize basic body function. The following parameters were collected: height (cm), weight (kg), body temperature ($^{\circ}\text{C}$), pulse rate, systolic and diastolic blood pressure (mmHg).

Data handling

Vital signs collected on treatment will be summarized. Values measured outside of on treatment period will be flagged in the listings.

Data analysis

For analysis of vital signs the clinically notable vital sign criteria are provided in [Table 2-10](#) below.

Table 2-3 Clinically notable changes in vital signs

Vital sign (unit)	Clinically notable criteria	
	above normal value	below normal value
Weight (kg)	increase > 10% from Baseline	decrease > 10% from Baseline
Systolic blood pressure (mmHg)	>=180 with increase from baseline of >=20	<=90 with decrease from baseline of >=20
Diastolic blood pressure (mmHg)	>=105 with increase from baseline of >=15	<=50 with decrease from baseline of >=15
Pulse rate (bpm)	>=100 with increase from baseline of >25%	<=50 with decrease from baseline of > 25%
Body temperature	>= 39.1	-

The number and percentage of subjects with notable vital sign values (high/low) will be presented.

In addition, values and change from baseline of vital signs will be summarized at each visit by descriptive statistics including mean, SD, median, 25th and 75th percentiles, minimum, and maximum.

A listing of all vital sign assessments will be produced and notable values will be flagged. In the listing, the assessments collected outside of on-treatment period will be flagged.

